1.0 Objectives

1.1 Purpose: To characterize motor cortex neurophysiology and to understand how one form of non-invasive brain stimulation (NIBS) called transcranial direct current stimulation (tDCS) changes brain excitability and behavior in children diagnosed with cerebral palsy, as compared to children with typical development (CTD).

Aim 1: Using transcranial magnetic stimulation (TMS), characterize brain excitability, specifically interhemispheric inhibition, in children with CP and CTD.

Aim 2: Evaluate the immediate effect of tDCS on brain excitability and motor performance in children with UCP and CTD.

Aim 3: Compare the responses to tDCS in each with individual estimated electric field intensity from computational modeling.

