At the moment, it is unclear what the acute effects of a single session tDCS are, when paired with motor training, on brain excitability or motor performance in children with and without UCP. This leads us to designing the proposed study, which will offer insight into the mechanisms of tDCS and lead the field toward a better understanding of how tDCS be implemented in a neurorehabilitation setting for both children and potentially adults.

2.2 Preliminary Data: Data from our previous study using TMS demonstrates the potential effect of cathodal tDCS to decrease cortical excitability. In a subset of 10 children, five of who received real stimulation and five received sham stimulation, we observed a decrease in motor evoked potential (MEP) amplitude following the two-week intervention period (Figure 1). These results indicate a potential neurophysiologic effect on the non-lesioned hemisphere using a small dose (0.7 mA) of tDCS. No effects on the excitability of the lesioned hemisphere were noted.

[figure not shown]

Figure 1. Change in brain excitability following tDCS. Children receiving cathodal tDCS (red line) showed a decrease in excitability compared to those in the sham group (black line).

2.3 Existing Literature: In one study of children with UCP, Kirton et al. used repetitive TMS to down-regulate the non-lesioned hemisphere, thereby decreasing IHI, in an effort to improve function of the more-affected upper limb.⁹ They found increases in grip strength in a small sample after the real intervention compared to a sham intervention. The same group also explored IHI in CTD, showing that IHI decreased with age and was correlated with unimanual performance.

The proposed study will, at the moment, be the first to offer comprehensive data specifically on interhemispheric inhibitory control mechanisms in children with UCP. We predict that children with intact functional connections from the lesioned hemisphere will show IHI, while those with only connections from the non-lesioned hemisphere will not.

The neurophysiologic effects of tDCS have not been widely reported in children with UCP. One study showed an increase in lesioned hemisphere excitability following anodal tDCS following 10 sessions of combined motor training and tDCS.¹⁰

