3.0 Study Endpoints/Events/Outcomes

- 3.1 Primary Endpoint/Event/Outcome: The primary outcome is magnitude of brain excitability as measured by motor evoked potentials from TMS. The primary behavioral outcome is time to complete a novel movement task.
- 3.2 Secondary Endpoint(s)/Event(s)/Outcome(s): The secondary neurophysiological outcomes are interhemispheric inhibition as measured by ipsilateral silent period (iSP) and paired pulse (PP) TMS (see 5.2 Study Procedures). The secondary behavioral outcomes are the Box and Blocks Test and Grip Strength. Safety and tolerability of the study, as measured through our participant-report of symptoms questionnaires, are also secondary outcomes.

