MRIs will be performed at the CMRR on the University of Minnesota campus. We will obtain a structural image of brain anatomy to be used for stereotactic neuronavigation and individual brain modeling described below (Pre-Test Assessment: TMS and Computational Modeling).

Children and their caregivers will be screened using pre-approved CMRR safety screening forms. Children will change into scrubs and be given a "tour" of the scanning facility room. In our experience, this can alleviate anxiety related to MRI scanning in children. Caregivers will be allowed to watch through the control room window.

When ready, children will lie on the scanner bed comfortably with cushioning, pillows, etc. A movie of their choice will be projected behind them to watch during the scan. Scanning will consist of a localizer sequence (< 1min), and a T1-weighted magnetization prepared rapid acquisition gradient echo (MP-RAGE) sequence (spatial resolution 1 mm isotropic, < 6min), T2-weighted fast low-angle shot (FLASH) sequence (spatial resolution 0.7x0.7x4.0 mm, < 6min), a pair of diffusion scans (spatial resolution 1.5 mm³), a task fMRI blood oxygen-dependent level (BOLD) scan and a resting-state fMRI BOLD scan (spatial resolution 2mm³, TR = 0.8s, MB = 8). If image quality is not deemed acceptable, we will repeat the T1-sequence as needed. Children will be able to talk to the scan operator at any time.

Day of Study

Location: Non-invasive Neuromodulation Lab—Clinical and Translational Science Institute (CTSI) or Pediatric Brain Stimulation Lab—Center for Neurobehavioral Development (CNBD)

Time: 3 hours

Pre-Test Assessment: TMS

All procedures will be performed on the non-lesioned, then lesioned hemisphere unless noted otherwise.

- A. Motor threshold (MT): To find the motor threshold, we will begin testing at the estimated location of the hand region of motor cortex as identified on the reconstructed brain image in the stereotactic neuronavigation system. We will test at 50% MSO. The motor threshold, is defined as the lowest stimulator output that produces MEPs of at least 50 μ V on 50% (i.e. 5 of 10) trials. The location associated with the motor threshold is denoted as the motor hotspot. We will test up 100% MSO if tolerated by the participant to determine a motor threshold.
- B. MEP Amplitude: Twenty pulses will be delivered at the motor hotspot using a testing intensity equivalent to 120% of the MT.

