- C. Cortical Silent Periods: Twenty pulses will be delivered at the motor hotspot using a testing intensity equivalent to 120% of the MT with the target hand muscle activated.
- D. Paired-Pulse Assessment: Using two TMS coils, a conditioning stimulus will be delivered to one hemisphere at an intensity equivalent to 100% MT. Simultaneously, a test stimulus will be delivered to the opposite hemisphere at an intensity equivalent to 120% RMT. A total of 20 pairs of stimuli will be used (10 with interstimulus interval = 10 ms, ten with interstimulus interval = 0 ms), delivered in a pseudorandom order.

Pre-Test Assessment: Behavioral

We will use the Gross Motor Function Classification Scale Score (GMFCS), and the Manual Ability Classification System (MACS) as clinical characterization of each participant. Members of the research team will assess hand function using the following measures: Assisting Hand Assessment (AHA), Box and Blocks Test, Grip Strength Dynamometry, and Jebsen Taylor Test of Hand Function (JTTHF). A novel motor performance task will also be employed to assess motor performance and potential effects of tDCS on motor learning.

Intervention

The intervention will last a total of 30 minutes, including preparatory time. Before stimulation, the area of skin underneath the electrode will be inspected for abrasions/lesions and then cleaned with an alcohol swab. We will use an M1-SO electrode montage, where one tDCS electrode is placed on the motor hotspot (M1) as determined by TMS testing, and the other electrode is placed on the supraorbital prominence (SO) of the opposite side. Sanitized rubber electrodes housed in single-use, sterile 3 cm x 5 cm sponges moistened with saline will be placed on the stimulation sites and held in place by elastic bands. To ensure adequate electrical conductance, care is taken to maintain firm contact of the sponge to the scalp. The static

impedance measurement is checked and stimulation does not proceed unless levels are within limits recommended by the tDCS device manufacturer.

Children in the sham group will receive the same procedures as the active tDCS group, yet the device will be set to an integrated sham setting which extinguishes the current after a 30 second to 1 minute ramp-up phase and gradually reintroduces the ramp-down at the end of the 20 minute session.

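### The paired-pulse block has no interleaved test-alone pulse, and the plan gives no reference condition or formula for paired-pulse interhemispheric inhibition

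*Combined protocol and SAP*

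**What the plan says.** Section 5.2, Pre-Test Assessment: TMS, item D describes a two-coil test in which "a conditioning stimulus will be delivered to one hemisphere at an intensity equivalent to 100% MT". The next sentence is "Simultaneously, a test stimulus will be delivered to the opposite hemisphere at an intensity equivalent to 120% RMT". The trials are then listed: "A total of 20 pairs of stimuli will be used (10 with interstimulus interval = 10 ms, ten with interstimulus interval = 0 ms", in pseudorandom order.

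Item B of the same section collects single pulses with no conditioning: "Twenty pulses will be delivered at the motor hotspot using a testing intensity equivalent to 120% of the MT". The list of procedures opens with the rule "All procedures will be performed on the non-lesioned, then lesioned hemisphere unless noted otherwise". TMS is repeated at 0, 15, 30 and 60 minutes after the intervention.

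Section 3.2 makes "interhemispheric inhibition as measured by ipsilateral silent period (iSP) and paired pulse (PP) TMS" a secondary outcome. Aim 1 in section 1.1 is to "characterize brain excitability, specifically interhemispheric inhibition, in children with CP and CTD". Section 2.1 explains IHI as the effect that activating one motor cortex has on the other. Section 2.3 predicts IHI in children whose lesioned hemisphere keeps functional connections, and says that "those with only connections from the non-lesioned hemisphere will not".

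Sections 15.1 and 15.3 cover neurophysiologic measures only in general terms. Neither gives a numerator, a denominator or a reference condition for paired-pulse IHI.

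**The concern.** On the protocol's own account, IHI is a contrast between the test response with and without prior activation of the other hemisphere. Item D supplies only the first half of that contrast. The other condition in the block, the 0 ms pair, also fires the conditioning coil, so its response need not equal the unconditioned one.

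Two analysts could therefore compute different IHI values from the same recordings, one dividing by the 0 ms pairs and the other by the item B pulses. The first choice carries an unknown effect of simultaneous stimulation. The second carries any change in excitability between the two blocks. That matters most after tDCS, when a change in excitability is the very thing under study: a shift between blocks that differed between real and sham stimulation would be read as a change in IHI.

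**Working it through.** **1. Trial count.** Item D gives 10 pairs at 10 ms and 10 at 0 ms. 10 + 10 = 20, which reproduces the stated total. Test-alone trials in the block: 20 − 10 − 10 = 0.

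**2. Using the 0 ms pairs as reference.** Let r = MEP(10 ms) / MEP(test alone), the quantity wanted, and f = MEP(0 ms) / MEP(test alone). Then

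observed ratio = MEP(10 ms) / MEP(0 ms) = r/f.

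The documents give no f, and block D does not measure it. Over an assumed range:

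| f (assumed) | 0.8 | 0.9 | 1.0 | 1.1 | 1.25 | 1.5 |
|---|---|---|---|---|---|---|
| r = 1.0 (no inhibition) | 1.25 | 1.11 | 1.00 | 0.91 | 0.80 | 0.67 |
| r = 0.8 | 1.00 | 0.89 | 0.80 | 0.73 | 0.64 | 0.53 |
| r = 0.6 | 0.75 | 0.67 | 0.60 | 0.55 | 0.48 | 0.40 |

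With f above 1, inhibition is overstated. With f below 1, it is understated: a true ratio of 0.8 disappears at f = 0.8. At f = 1 there is no bias.

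**3. One way f could exceed 1.** Suppose the conditioning pulse evokes its own response C in the recorded hand, which adds to the test response T at 0 ms but not at 10 ms. Then f = (T + C)/T, and with no true inhibition the observed ratio is T/(T + C). T and C are assumed. The lower value of C, 0.05 mV, equals the 50 microvolt criterion in the motor-threshold definition.

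| T (mV) | C = 0.05 mV | C = 0.2 mV |
|---|---|---|
| 0.2 | 0.2/0.25 = 0.80 | 0.2/0.4 = 0.50 |
| 0.5 | 0.5/0.55 = 0.91 | 0.5/0.7 = 0.71 |
| 1.0 | 1.0/1.05 = 0.95 | 1.0/1.2 = 0.83 |

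Testing the lesioned hemisphere, this needs a child with both a crossed projection from that hemisphere (so that a test MEP exists) and an uncrossed projection from the other.

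**4. Using item B as reference.** Here f drops out. If the test-alone response during block D is d times its level during block B, the observed ratio is r × d. With r = 1, d = 0.9 gives 0.90 and d = 1.1 gives 1.10. The documents give no value for d. The nominal intensities match only if MT (item B) and RMT (item D) are the same, which is not stated.

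**5. Using interleaved test-alone pulses.** The ratio is r whatever f is, and slow drift affects numerator and denominator alike.

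**6. Precision.** Treating trials as independent with a common coefficient of variation CV (assumed), the standard error of the log ratio is about CV × √(1/10 + 1/n), where n is the number of reference pulses. At CV = 0.6 this is 0.268 with 10 interleaved pulses and 0.232 with the 20 pulses of item B.

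**The case against.** The strongest reply is that the session does contain unconditioned pulses. Item B gives 20 per hemisphere at the same nominal intensity, and since TMS is repeated after tDCS they are plausibly available at each time point. On that view the gap is a missing definition rather than a missing measurement. Much of this stands: a reader might infer from item D that the trial has no valid reference for IHI at all, and the documents do not support that. What remains is that the plan never links item B to the paired-pulse measure, and that a separate block is open to drift.

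It is also fair to say that no section makes the 0 ms pairs the denominator, and that the bias could run either way. A reader might take the illustration in step 3 to mean 20–50% false inhibition. That range belongs to the smallest test MEP assumed; at 1.0 mV the same assumptions give 5–17%. The amplitudes and their simple addition are assumed, and the 50 microvolt rule belongs to the muscle used to set threshold, not necessarily to the opposite hand.

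A reader might further infer that the artefact undermines the wiring prediction in section 2.3. That goes too far. Children with connections only from the non-lesioned hemisphere have no lesioned-hemisphere test MEP, so no ratio exists in that direction. In the other direction, a hemisphere without motor output adds no conditioning response. The mechanism is confined to children with both kinds of projection, a group the plan neither defines nor counts.

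Finally, a bias that is stable within a child would tend not to favour real or sham tDCS in a randomized comparison of change. That limits the 0 ms problem mainly to the descriptive Aim 1. It does not cover drift that differs between groups.

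**Conclusion.** The point holds as a defect in how one secondary measure is specified. All 20 trials are conditioned, no test-alone pulse is interleaved, and neither a reference nor a formula is given. Under a 0 ms reference, the observed ratio for a child with no inhibition runs from 1.25 to 0.67 as f runs from 0.8 to 1.5. That range of f is assumed, so this is an illustration and not an estimate of bias in this trial. Under an item B reference, the error equals whatever drift occurs between blocks, which the documents do not quantify.

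The ipsilateral silent period is a separate IHI measure and does not depend on this block. The primary MEP outcome, its power calculation and its significance level are also untouched. The description of the two stimuli as simultaneous fits only the 0 ms half of the trials, and the mixture of MT and RMT leaves it unclear whether items B and D use the same intensity.

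**What to change.** In section 5.2, item D, replace the ten 0 ms pairs with ten test-alone pulses at the block's test intensity, with the conditioning coil in place but not fired, interleaved in the same pseudorandom sequence as the ten 10 ms pairs. In section 15, define IHI as the mean conditioned (10 ms) MEP divided by the mean test-alone MEP from that sequence, at each time point and in each direction where a test MEP can be obtained.

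If the 0 ms pairs are kept, name item B as the reference, write the ratio on that basis, and acknowledge its exposure to drift.

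In either case, reconcile the word for simultaneous delivery with the 10 ms interval, and MT with RMT.

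The cost is protocol wording. The sequence stays at 20 trials, so time should not change, and ten fewer conditioning pulses are given. The 0 ms condition is lost, though the plan states no use for it. Ten interleaved reference pulses are also somewhat less precise than the 20 in item B (step 6), which is a reasonable price for removing both f and between-block drift.

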6.0 Data and Specimen Banking

- 6.1 Storage and Access: Urine specimens will be obtained for pregnancy testing (Icon 25HCG One-Step, Beckman Coulter, Brea, CA) of all pubescent females and immediately used for assessment of pregnancy status. Specimens are discarded at the CTSI through specimen procedures.

- 6.2 Data: No data elements will be collected and banked

- 6.3 Release/Sharing: The results of pregnancy tests, if positive, will not be shared with the participant or his/her caregiver. Instead, they will be informed that they no longer meet the inclusion/exclusion criteria to continue in the study.

7.0 Sharing of Results with Participants

- 7.1 This study is not designed to produce a direct benefit to the participant. We will not share specific individual results with participants and families. At the time of publication of any manuscripts associated with this study, we will send a lay summary and a copy of the article to each participant and their family.

8.0 Study Population

- 8.1 Inclusion Criteria: Participants with UCP must have a clinical diagnosis of cerebral palsy with confirmed radiologic evidence of hemispheric stroke or periventricular leukomalacia.

All participants (UCP and CTD) will be eligible if they meet all of the following criteria:

1. Aged between 7 years 0 days and 21 years, 355 days (see *10.2 Vulnerable Populations*)
2. Able to give informed assent (if under 18 years of age)
3. Able to follow 2-step commands
4. Presence of an MEP in the less affected (UCP) or non-dominant (CTD) hand when stimulating the non-lesioned hemisphere

8.2 Exclusion Criteria: Participants will be excluded if they meet any of the following criteria:

1. Evidence of a seizure within the past two years
2. Other neurological or metabolic conditions/diagnoses
3. Treatment with injectable agents (e.g. Botox) for spasticity management
4. Is pregnant (females only)
5. Presence of indwelling metal in the head (e.g. aneurysm clip) or medical device. Dental braces are allowable if approved by the CMRR safety monitor and PI.

8.3 Screening: Participants will be rigorously screened against inclusion/exclusion criteria to ensure that their participation is safe. This screening begins at the initial discussion in the phone screen, continues with review of the medical record by the PI and Medical Director, and is again repeated in-person by reviewing the medical record (Appendix D). All pubescent (verification of menstrual cycle from caregiver/parent) female participants will need to take a urine pregnancy test. If the test is positive, the participant will be excluded from the study as the safety of use of tDCS and TMS during pregnancy has not been established.

The research team will utilize the CMRR Center's screening tools and adhere to the screening SOP during enrollment of all research participants in this protocol. The CMRR Center's screening tools and SOP are IRB approved under the CMRR Center Grant (HSC# 1406M51205) and information regarding screening procedures is publically available on the CMRR website.

9.0 Vulnerable Populations

9.1 Vulnerable Populations:

- Children
- Pregnant women/Fetuses/Neonates
- Prisoners

- Adults lacking capacity to consent and/or adults with diminished capacity to consent, including, but not limited to, those with acute medical conditions, psychiatric disorders, neurologic disorders, developmental disorders, and behavioral disorders
- Approached for participation in research during a stressful situation such as emergency room setting, childbirth (labor), etc.
- Disadvantaged in the distribution of social goods and services such as income, housing, or healthcare
- Serious health condition for which there are no satisfactory standard treatments
- Fear of negative consequences for not participating in the research (e.g. institutionalization, deportation, disclosure of stigmatizing behavior)
- Any other circumstance/dynamic that could increase vulnerability to coercion or exploitation that might influence consent to research or decision to continue in research
- Undervalued or disenfranchised social group
- Members of the military
- Non-English speakers
- Those unable to read (illiterate)
- Employees of the researcher
- Students of the researcher
- None of the above

9.2 Additional Safeguards: We are studying children and young adults aged 7-21 with a specific diagnosis of cerebral palsy. As we are a pediatric laboratory with experienced pediatric researchers, clinicians and trainees, comprehensive efforts have been made to ensure that our procedures are developmentally appropriate to both child and family. Recruitment materials, study information, and conversations are tailored to a pediatric population. Participant-specific study materials are provided before participation in interventions and testing sessions, and age-appropriate adaptations for each procedure/test are used. Our team has created videos that help explain the research and procedures to families. These videos can be viewed at any time before enrolling or participating in the study. ([[name] Lab Video](#); [TMS Video](#)). We also have a network of past participant families who have offered to share their experiences in our research studies with potential participants.

For MRI testing, we introduce children to the MRI environment with a mock scanner, consisting of a “tunnel” in which children can lie. This provides an indication of the dimensions of the actual scanner. We will provide audio files of scanner sounds to familiarize children with MRI sounds. During the actual scan, children can watch a movie or listen to music. Although the caregivers will have the ability to see their child in the scanner from the control room, if necessary, a caregiver may stay with the

child in the scanner room (assuming the caregiver meets all MRI safety criteria). Children and families will be given the opportunity to tour the TMS testing intervention rooms to ask questions about the equipment and technology.

During the intervention and testing session, behavioral and environmental strategies will be implemented for all children to optimize tolerance and completion of each session. These may include but are not limited to: predictable routines, visual timer, distraction techniques, child-friendly descriptive language, and positioning.

Our team is trained to be attentive to the child's mood and comfort, which are important factors when asking children to engage in long testing sessions. Throughout their participation, the research team will continually check in with the participants for real-time verbal feedback on their experience. We recognize the value and importance of feedback from children and families about their experience during the study, and have developed surveys to collect this type of information (Appendix G). We will continue to adapt study procedures based upon this feedback. We will provide drinks and snacks throughout the child's participation in the study and provide breaks as necessary.

For non-English speaking participants, we will work with the IRB and other community groups to provide all information in the participant's native language.

